### 1.3. Safety Endpoints

The safety and tolerability endpoints are as follows:

- occurrence of adverse events during the study
- clinically significant changes in physical examinations, including body weight

Statistical Analysis Plan

- clinical laboratory (serum chemistry, hematology and coagulation, and urinalysis) test results at each visit
- vital signs (blood pressure, respiratory rate, body temperature, and pulse) measurements at each visit  
Note: Oxygen saturation and respiratory rate will be measured in cases of suspected anaphylaxis and severe hypersensitivity.
- 12-lead electrocardiogram (ECG) findings at each visit
- use of concomitant medication during the study
- number (%) of patients who did not complete the study (day 168, end of study)
- number (%) of patients who did not complete the study due to adverse events
- local tolerability at the injection site (ie, erythema, induration, ecchymosis, and pain) at the following time points postdose: day 0, day 28, and day 56
- hypersensitivity reaction assessment
- Columbia Suicide Severity Rating Scale (C-SSRS)

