## 1.6. Estimand for Primary Efficacy Endpoint

The primary estimand for this study is defined by the following 4 components:

1. **Target population:** male and female patients aged 18 to 70 years, inclusive, with a history of PTH (as defined by International Classification of Headache Disorders 3rd revision [ICHD-3] (beta version) criteria).
2. **Outcome measure:** mean change from baseline (baseline period) in the monthly average number of headache days of at least moderate severity during the 12 week period after the first dose of the IMP.
3. **Analysis set and handling of intercurrent events:** The full analysis set (FAS) will be used for efficacy analyses. FAS is a subset of the ITT analysis set including only patients who received at least 1 dose of IMP and had at least 1 post-baseline efficacy assessment on the primary endpoint. In the FAS, treatment will be assigned based on the treatment to which patients were randomized, regardless of which treatment they actually received.

For patients randomized to active treatment who did not complete the double-blind treatment period due to lack of efficacy, death, or adverse event, the average number of headache days in the remainder of the analysis window will be imputed as the mean monthly average of headache days in the same analysis window for patients assigned to placebo.

All other missing data for patients in either treatment group will be handled as follows:

- For patients who have  $\geq 10$  days of e-diary data in an analysis window, the monthly average number of headache days will be calculated based on data available in that analysis window and prorated to 28 days
- For patients who have  $< 10$  days of e-diary data in an analysis window, the monthly average number of headache days will be imputed using the mean monthly average of

headache days in the same analysis window for patients assigned to the same treatment group and having  $\geq 10$  days of e-diary data.

More details are provided in Section [6.1.4](#).

4. **Measure of treatment effect:** analysis of covariance model including treatment as fixed effect and the baseline number of headache days of at least moderate severity and the posttraumatic headache onset ( $< 12$  months and  $\geq 12$  months) as covariates.

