### **2.5. Sequence of Planned Analyses**

#### **2.5.1. Planned Interim Analyses**

There will be no interim analysis. However, a database lock from the double-blind period will occur following the completion of visit 5 by the last patient. Unblinding will occur after the database lock from the double-blind treatment period.

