#### **2.5.2. Final Analyses and Reporting**

A database lock from the double-blind treatment period will occur following the completion of visit 5 by the last patient. Unblinding will occur after the database lock from the double-blind treatment period. This SAP will be finalized before the database lock.

All endpoints related to the double-blind treatment period will be analyzed, including data up to visit 5.

Data collected from open-label treatment period (visit 5 and after) will be analyzed separately after study completion.

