### **5.2. Patient Disposition**

Data from patients screened; patients screened but not randomized and reason not randomized; patients randomized (ITT); patients randomized but not treated; patients in the safety and other analysis sets; patients who completed the double-blind treatment; patients who enter open-label treatment period; patients who did not complete double-blind treatment will be summarized using descriptive statistics. Data from patients who did not complete double-blind treatment will also be summarized by reason using descriptive statistics.

This summary will include all patients.

Patients who completed study or patients withdrew from the study by reason will be summarized once the study is completed.

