#### 6.1.4. Handling Missing E-diary Data

This section includes missing data handling for e-diary data. For other type of data, the missing data handling methods are provided in the analysis section for the endpoint if applicable.

**For analyses using ANCOVA or mixed model for repeated measures (MMRM)** based on monthly averages the missing data handling methods are as follows:

For patients randomized to active treatment group and did not completed the double-blind treatment period due to lack of efficacy, death, or adverse event, the number of headaches in an analysis window will be imputed as the following

$$\sum (\text{observed headaches during a analysis window}) + (N-X) * (\text{placebo average}/N)$$

Where

$N$  denotes the number of days in the analysis window, 84 days for 12-week analysis window and 28 days for 4-week analysis window;

$X (X > 0)$  denotes the number of days with e-diary within the analysis window;

“Placebo average” is the monthly average of number of headache during the analysis window from placebo patients who completed study.

For 12-week analysis window, the monthly average of the number of headaches will be prorated to 28 days using formula A;

All other missing data for patients in either treatment group will be handled as follows:

- For patients who have  $\geq 10$  days of e-diary data in an analysis window, the monthly average number of headache days will be calculated based on data available in that analysis window and prorated to 28 days using formula A;
- For patients who have  $< 10$  days of e-diary data in an analysis window, the monthly average number of headache days will be imputed using the mean monthly average of headache days in the same analysis window for patients assigned to the same treatment group and having  $\geq 10$  days of e-diary data.

**Note: the imputation is only for post-baseline data and applies to all efficacy endpoints related to the number of headache days.**

In addition, as a sensitivity analysis, the primary endpoint will be analyzed using a MMRM method. Detail is provided in Section 6.2.3.

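### SAP 6.1.4 fills in fremanezumab drop-outs from placebo completers only, against the SAP's own estimand and the protocol; the effect is probably small

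*SAP*

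**What the plan says.** SAP 1.6 defines the primary estimand. For fremanezumab patients who leave double-blind treatment for lack of efficacy, an adverse event or death, the rest of the window "will be imputed as the mean monthly average of headache days in the same analysis window for patients assigned to placebo". Protocol 9.5.5.1 names the same reference group. Neither requires those placebo patients to have completed anything.

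SAP 1.6 then refers to 6.1.4 for details. There the fremanezumab patients concerned are those who "did not completed the double-blind treatment period due to lack of efficacy, death, or adverse event", and the placebo average used to fill their missing days "is the monthly average of number of headache during the analysis window from placebo patients who completed study".

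Three other SAP sections bear on the meaning of that phrase:

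- Section 1.3 ties completion of the study to day 168.
- Section 5.2 tabulates completion of double-blind treatment separately and adds: "Patients who completed study or patients withdrew from the study by reason will be summarized once the study is completed".
- Section 2.5.2 sets the timing of the double-blind analysis: "A database lock from the double-blind treatment period will occur following the completion of visit 5 by the last patient".

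SAP 17, on changes from the protocol's analyses, says there are none.

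**The concern.** The placebo fill exists so that fremanezumab is not credited with benefit in patients whom it failed. Its value depends on who supplies the placebo mean. Restricting that group to completers conditions on something that happens after randomisation. A placebo patient who leaves for lack of efficacy, which protocol 3.4 names as a reason for leaving, contributes diary data under 1.6 but none under 6.1.4. If such patients have more headache days than those who stay, the completer mean is too low and the fill is too kind to fremanezumab.

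The planned sensitivity analysis would not show this. SAP 6.1.4 applies the same imputation to the ANCOVA and the MMRM, and its note extends it to every endpoint based on the number of headache days. The 50% responder analysis in 6.3.1 also refers to it.

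Whatever the size, the primary analysis has two incompatible pre-specified rules. Choosing between them after unblinding would be a choice made with the data in view.

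**Working it through.** **1. The reference sets side by side.**

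| Place | Placebo patients supplying the mean |
|---|---|
| Protocol 9.5.5.1 | assigned to placebo |
| SAP 1.6 | assigned to placebo |
| SAP 6.1.4 | placebo, and completed the study |

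The SAP introduction says that the SAP prevails where it differs from the protocol. That cannot settle a conflict between two sections of the SAP.

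**2. What completing the study means.** SAP 1.3 and 5.2 use it for the end of the study (day 168, visit 8), apart from completion of double-blind treatment. SAP 6.1.4 itself speaks of the double-blind treatment period when it describes the fremanezumab patients. On that usage, visit 8 falls 168 − 84 = 84 days after visit 5. At a lock triggered by the last patient's visit 5, the status is undetermined for the last patient and for anyone else still short of visit 8. It also depends on whether placebo patients stayed through 12 weeks of open-label fremanezumab.

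**3. The plan's own figures.** The protocol's sample-size text, given as new wording in its Amendment 02 summary of changes, assumes a difference of 2.0 days, SD 4.4, 80% power, two-sided 5% and 10% discontinuation. A two-sample t-test needs 76.9, so 77 per arm (154). Then 77 / 0.90 = 85.6, so 86 per arm (172). Both match. No stated figure depends on the placebo-average rule, so 2.0 days serves only as a yardstick.

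**4. Size of the shift.** Let q be the placebo drop-out proportion, d the excess headache days per 28 in placebo drop-outs over completers, f the proportion of fremanezumab patients filled, and m the share of their window missing. If completers average μ, all placebo patients average (1 − q)μ + q(μ + d) = μ + qd. So:

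- reference too low by q × d
- treatment difference moved by f × m × q × d

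Only q = 10% has a basis in the documents (the planning rate). The other values are assumptions.

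| q | d | q × d | f | m | shift in difference (days) |
|---|---|---|---|---|---|
| 0.10 | 2 | 0.2 | 0.05 | 0.67 | 0.007 |
| 0.10 | 6 | 0.6 | 0.10 | 0.67 | 0.04 |
| 0.20 | 6 | 1.2 | 0.10 | 0.67 | 0.08 |

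With wider assumptions (q 5% to 30%, d 2 to 8, f 5% to 20%, m 50% to 67%) the shift runs from 0.05 × 0.50 × 0.05 × 2 = 0.0025 to 0.20 × 0.67 × 0.30 × 8 = 0.32 days. With 87 patients split 1:1, the unadjusted standard error of the difference is 4.4 × √(4/87) = 0.94 days, so 0.08 is under a tenth of one standard error.

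These figures take the daily placebo rate as the 28-day average divided by 28. The formula in 6.1.4 divides by 84 for the 12-week window. If the total is then averaged over 84 days, the shifts are one third as large. That scaling is a separate matter.

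**5. Whether a 10-day diary condition changes the reference.** Under 6.1.4, a placebo patient with fewer than 10 diary days receives the mean M of placebo patients with 10 or more. With n₁ patients averaging M and n₀ given M, the mean over all is (n₁M + n₀M) / (n₁ + n₀) = M, so it is unchanged.

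**The case against.** The strongest reply is that the phrase is loose drafting for completing double-blind treatment. The rule sits among 12-week windows, and SAP 2.5.2 and 6.1 require it to run at the double-blind lock on data up to visit 5. That reading is plausible. If it is right, the timing point and the dependence on open-label retention both fall away. The completer restriction and the conflict with 1.6 remain.

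A second reply is that 1.6 defers to 6.1.4, so 6.1.4 merely says which placebo patients are meant. But adding a completion condition changes the reference group, and SAP 17 still declares no change from the protocol.

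A third is that a 10-day diary condition is also post-randomisation and is absent from the reference sentence in 1.6. It does leave out the few observed days of the earliest placebo drop-outs. But the SAP already applies this threshold to each arm, and step 5 shows that under that rule it gives the same mean as all FAS placebo patients.

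The small size is conceded.

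**Conclusion.** The contradiction is certain: it stands in the wording of SAP 1.6 and 6.1.4, sets 6.1.4 against the protocol, and is undisclosed in SAP 17. The completer rule conditions on a post-randomisation outcome. The consequence is probably small, about 0.01 to 0.08 days against 2.0 under the assumptions in the first table of sizes. If placebo drop-outs do not differ from completers it is zero. This is mainly a defect of pre-specification, and worth correcting because the correction is so cheap.

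A reader might infer two stronger things.

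- *That the error always favours fremanezumab.* That needs placebo drop-outs to do worse, and the documents report no outcomes for them. On the visit 8 reading, the rule also removes placebo patients who finished 12 blinded weeks and left during open-label treatment; there the direction is unclear.
- *That the placebo reference is simply unknown at the double-blind lock.* That holds only on the visit 8 reading, and then only for patients short of visit 8. How many is not known: 17 of the 87 were randomised after the 70 reported at Amendment 01, but without the last randomisation date this is not a firm upper bound.

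**What to change.** In SAP 6.1.4, define the placebo average from all FAS patients randomised to placebo with at least 10 days of e-diary data in that analysis window. State the same set in 1.6, and finalise both before the double-blind lock. Membership then rests only on data available at that lock, and completion status no longer matters on either reading. The completer version could be kept as a labelled sensitivity analysis.

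The cost is one phrase in 6.1.4 and a matching one in 1.6. No further data are needed, and sample size and power are unaffected.

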## 9.5.5.1. Primary Efficacy Analysis

The primary efficacy endpoint for this study will be derived from PTH data (ie, presence of headache [yes/no] and peak severity [mild/moderate/severe]) collected daily using an electronic headache diary application.

The primary endpoint will be analyzed using an analysis of covariance (ANCOVA) method. The model will include treatment as fixed effect and the baseline number of headache days of at least moderate severity and the PTH onset (<12 months and ≥12 months) as covariate. A 95% confidence interval will be constructed for the least squares mean difference between the fremanezumab group and the placebo group, and the p-value will be presented.

The primary estimand for this study is defined by the following attributes:

- The target population includes male and female patients aged 18 to 70 years, inclusive, with a history of PTH (as defined by the ICHD-3 [beta version] criteria).
- The primary outcome measure is the mean change from baseline (baseline period) in the monthly average number of headache days of at least moderate severity during the 12-week period after the first dose of IMP.
- The FAS will be used for efficacy analyses. FAS is a subset of the ITT analysis set and includes only patients who receive at least 1 dose of IMP and have at least 1 postbaseline efficacy assessment on the primary endpoint. In the FAS, treatment will be assigned based on the treatment to which patients were randomized, regardless of which treatment they actually received.
- Treatment effect will be measured via ANCOVA method, including treatment as fixed effect and the baseline number of headache days of at least moderate severity and the PTH onset (<12 months and ≥12 months) as covariates.

For patients assigned to active treatment who discontinue the study due to lack of efficacy, death, or adverse event, the proportion of headache days in the remainder of the analysis window will be imputed as the mean monthly average of headache days in the same analysis window for patients assigned to placebo. All other missing data for patients in either treatment group will be handled as follows:

- For patients who have ≥10 days of e-diary data in an analysis window, the monthly average number of headache days will be calculated based on data available in that analysis window and prorated to 28 days.

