**6.1.3. Analysis Windows for E-diary Data**

**Baseline** window is the period from the day of the informed consent to before the administration of the first dose of the IMP. The baseline monthly average value for an efficacy variable will be calculated based on data recorded in the baseline window and prorated to 28 days using formula A.

**Postbaseline 4-week (monthly) analysis windows** will be determined based on the actual dosing date as follows:

- Month 1 (weeks 1 to 4): from the day of the first dose of the IMP administration to the day before the IMP administration at visit 3 (week 4/dose 2) or to the end of e-diary in the double-blind treatment period if a patient only receives dose 1;
- Month 2 (weeks 5 to 8): from the day of the IMP administration at visit 3 (week 4/dose 2) to the day before the IMP administration at visit 4 (week 8/dose 3) or to the end of e-diary in the double-blind treatment period if a patient only receives dose 1 and dose 2;

- Month 3 (weeks 9 to 12): from the day of the IMP administration at visit 4 (week 8/ dose 3) to the end of e-diary of the double-blind treatment period.

Notes:

1. The end of e-diary of the double-blind treatment period is defined as the date of last IMP administration + 27 days.
2. There will be no double-blind IMP administration at visit 5;
3. A 4-week analysis window may contain <28, 28, or >28 days.

The monthly average of an efficacy variable for each analysis window will be calculated based on data recorded in the e-diary and prorated to 28 days using formula A. Missing data handling methods are provided in Section 6.1.4.

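### For fremanezumab patients who stop for lack of efficacy, death or an adverse event, the SAP gives no placebo-based value for months whose dose was never given

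*SAP*

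**What the plan says.** SAP 6.1.3 builds three 4-week windows from actual dosing dates. Month 2 is counted "from the day of the IMP administration at visit 3 (week 4/dose 2") and Month 3 "from the day of the IMP administration at visit 4 (week 8/ dose 3"). It adds: "The end of e-diary of the double-blind treatment period is defined as the date of last IMP administration + 27 days". For a patient given only dose 1, or only doses 1 and 2, the section says where the last dosed window closes. It says nothing about the windows after that.

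SAP 6.1.4 then gives two rules.

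- **Placebo-based fill.** This is for patients randomized to fremanezumab who do not complete the double-blind period because of lack of efficacy, death or an adverse event. The window total is observed headaches + (N − X) × (placebo average / N). N is 28 for a 4-week window and 84 for the 12-week window. X is the number of diary days in the window and is required to exceed 0. The placebo average comes from placebo patients who completed.
- **Residual rule.** It opens with "All other missing data for patients in either treatment group will be handled as follows". With at least 10 diary days the observed rate is prorated. With fewer than 10, the value "will be imputed using the mean monthly average of headache days in the same analysis window for patients assigned to the same treatment group" who have at least 10 days.

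The section applies these rules to both ANCOVA and MMRM, and a note adds that "the imputation is only for post-baseline data and applies to all efficacy endpoints related to the number of headache days".

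On intent, SAP 1.6 says that for these patients "the average number of headache days in the remainder of the analysis window will be imputed as the mean monthly average" of placebo patients. Protocol 9.5.5.1 says "the proportion of headache days in the remainder of the analysis window will be imputed as the mean monthly average", again from placebo.

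The monthly windows feed the MMRM sensitivity analysis (SAP 6.2.3), the monthly responder endpoints (6.3.2) and the monthly mean-change endpoints (6.3.3). The primary ANCOVA uses one 12-week window (6.2.1).

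**The concern.** The plan treats fremanezumab patients who leave for these three reasons as reverting to placebo level. That is deliberately conservative. The two sections together do not carry it into a month that never opened: such a month has no start date, no countable diary days and so no X > 0. Two programmers could implement this differently and both be able to point to the text.

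Month 3 is the most exposed. Everyone who left before dose 3 is undefined there, and SAP 6.3.3 says the results from the last window will be presented. If fremanezumab works, the own-arm reading credits patients who left because it failed or harmed them with the average fremanezumab result. That choice should be written down before unblinding.

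**Working it through.** **1. Planning inputs.** Protocol Section 16.1 (the new wording given for Section 9.1) states a difference of 2.0 days, SD 4.4, 80% power, two-sided alpha 0.05, 77 evaluable patients per arm, 10% discontinuation and 172 randomized. A two-sample t-test calculation gives 76.95, so 77 per arm; 77/0.9 = 85.6, so 86 per arm and 172 in total. The plan's figures reproduce. Recruitment stopped at 87 patients (Protocol 3.2), so 1:1 allocation gives about 43 and 44 per arm.

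**2. Windows under SAP 6.1.3, with doses on nominal days 1, 29 and 57.**

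| Doses received | Month 1 | Month 2 | Month 3 |
|---|---|---|---|
| 1 | days 1-28 | undefined | undefined |
| 2 | days 1-28 | days 29-56 | undefined |
| 3 | days 1-28 | days 29-56 | days 57-84 |

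An undefined month has X = 0 by construction, even if the patient goes on recording after last dose + 27 days.

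**3. Which rule reaches it.** The placebo fill requires X > 0, so it does not. The rule for fewer than 10 days can be read to reach it (0 < 10) and returns the fremanezumab mean. If the residual rule is held not to cover these patients, no rule applies and the month is missing.

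**4. Started months and the primary analysis.** Take a patient who stops on day 20 after dose 1 with 20 diary days. In Month 1, X = 20, so 28 − 20 = 8 days are filled from placebo. In the 12-week window, X = 20, so 84 − 20 = 64 days are filled from placebo. Full analysis set members need at least one post-baseline assessment on the primary endpoint, so X > 0 holds over 12 weeks.

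**5. Size on the own-arm reading, compared with placebo fill.** Let q be the share of the fremanezumab arm leaving for the three reasons. The documents give no rate by reason, so q is assumed at 2.5%, 5% and 10%. The last is the all-cause planning rate and therefore a ceiling. Of 43 patients this is 1.1, 2.2 and 4.3. Assume also that leavers resemble stayers.

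- One affected month: q × 2.0 = 0.05, 0.10, 0.20 days.
- Months 1-3 average, all leaving after dose 1: q × 2.0 × 2/3 = 0.03, 0.07, 0.13 days.
- Months 1-3 average, all leaving after dose 2: q × 2.0 × 1/3 = 0.02, 0.03, 0.07 days.
- Standard error of a difference: 4.4 × √(1/43 + 1/44) = 0.944; 0.20/0.944 = 0.21.
- Responders: each patient reclassified moves the fremanezumab rate by 1/43 = 2.3 percentage points.

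**6. Sensitivity to the leavers assumption.** A large simulation at q = 10% took leavers as 1 SD worse, with within-patient correlations of 0.5 and 0.7 (all assumed). The Month 3 own-arm gap became 0.22 to 0.23 days. If the months are instead left missing, Month 3 is 0.20 days more favourable than placebo fill when leavers resemble stayers, but 0.01 to 0.10 days less favourable when they were 1 SD worse. The direction of the left-missing reading is therefore not fixed.

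**7. Check of the repair.** With N = 28, X = 0 and placebo average P, the formula gives 0 + (28 − 0) × P/28 = P.

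**The case against.** The strongest defence is that the SAP already means placebo fill. Its first rule is defined by patient and reason, so the word other in the residual rule naturally excludes these patients. The X > 0 condition sits only in a symbol definition, and without it the formula returns the placebo average. This stands as to likely intent, and it means the own-arm mean cannot be called the SAP's prescribed value. It does not close the gap, because the condition is written and the window has no definition. The estimand texts do not settle it either: both fill only the rest of a window, which presupposes one that has begun, and both describe the 12-week outcome.

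Second, MMRM accommodates missing months, and a sensitivity analysis may use a different drop-out assumption. Both are true. But SAP 6.1.4 says its rules apply to MMRM, and SAP 6.2.3 exists to explore the impact of missing data, so its assumption needs stating.

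Third, the effect is small and nothing in the fixed sequence depends on it. That stands and sets the weight of the point.

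A reader might infer that all of Months 2 and 3 lose the placebo fill once such a patient stops. They do not: a patient who stops in Month 2 after dose 2, with any diary day there, keeps it in Month 2, and one who stops after dose 3 has all three windows defined.

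**Conclusion.** The gap is real but minor. It covers only months whose dose was never given, in fremanezumab patients who permanently stop double-blind treatment for one of the three reasons. For those months the SAP leaves either the fremanezumab mean or no value, and does not choose.

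Exposed are the MMRM sensitivity analysis, the weeks 5-8 and 9-12 mean-change endpoints, and probably the matching monthly responder endpoints. SAP 6.3.2 follows 6.3.1, which points to 6.1.4, but it does not itself say that the imputation applies.

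A reader might go further and infer that the primary result or the confirmatory testing is biased. The documents do not support that. The primary ANCOVA and the 12-week responder endpoint rest on the 12-week window, HIT-6 is a questionnaire score, and SAP Section 7 places no monthly endpoint in the sequence.

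The size, 0.05 to 0.20 days in one month and about 0.2 standard errors at the ceiling, assumes the 2.0-day design effect, the stated range of leavers and leavers who resemble stayers. With no drug effect and leavers like stayers, the expected difference between the own-arm and placebo fills is zero.

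**What to change.** Amend the SAP before the double-blind lock:

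1. In 6.1.3, define months that were never started. Suggested wording: *For patients who permanently discontinue double-blind IMP before dose 2 or dose 3, each month not started is the next nominal 28-day period after the last dosed window, with X = 0. Patients who miss a dose but continue keep their recorded diary days, with windows split at the nominal visit day.* The second sentence prevents real Month 2 diary data being discarded for someone who misses dose 2 but receives dose 3.
2. In 6.1.4, change X > 0 to X ≥ 0 for the 4-week windows.
3. In 6.1.4, state that fremanezumab patients who stop for the three reasons are excluded from the own-arm rule for fewer than 10 days, and state whether the same handling applies to the monthly responders in 6.3.2.

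The cost is one symbol and a few sentences, with no new data. The monthly and MMRM estimates may become slightly less favourable to fremanezumab; the primary analysis does not change. The use of N = 84 as the divisor for a monthly placebo average in the 12-week formula does bear on the primary imputation. It should be raised as a separate finding and adds no weight here.

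### The 12-week placebo fill in SAP 6.1.4 divides a 28-day average by 84, so responder status and the primary value of active-arm discontinuers depend on how it is programmed

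*SAP*

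**What the plan says.** SAP 6.1.4 has two imputation rules for diary data.

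- **Placebo fill.** It applies "For patients randomized to active treatment group and did not completed the double-blind treatment period due to lack of efficacy, death, or adverse event". Observed headaches are added to (N−X) × placebo average / N. Here N "denotes the number of days in the analysis window, 84 days for 12-week analysis window and 28 days for 4-week analysis window", X "denotes the number of days with e-diary within the analysis window" and must exceed zero, and the placebo average "is the monthly average of number of headache during the analysis window from placebo patients who completed study". The text then adds: "For 12-week analysis window, the monthly average of the number of headaches will be prorated to 28 days using formula A". Formula A (SAP 6.1.2) divides by the days recorded in the diary.
- **Own-arm mean.** Otherwise, a patient with at least 10 diary days is prorated from own data. With fewer than 10, the value "will be imputed using the mean monthly average of headache days in the same analysis window for patients assigned to the same treatment group", taken from patients with at least 10 days.

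The lead-in names only ANCOVA and MMRM, but the Note says "the imputation is only for post-baseline data and applies to all efficacy endpoints related to the number of headache days". SAP 6.3.1 sends the CMH-tested 12-week responder endpoint to 6.1.4, 6.3.2 follows 6.3.1 for the monthly responder endpoints, and 6.2.1 sends the primary endpoint there. Formula B then gives the percentage reduction.

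Protocol 9.5.5.3 promises a 95% confidence interval for key secondary endpoints. SAP 6.3.1 lists counts, percentages and a p-value. SAP 17 declares no change from the protocol.

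**The concern.** In the 12-week window the scales do not match. The placebo average covers 28 days but is spread over 84, so each missing day receives a third of the placebo daily rate. The filled total is then sent to a formula whose denominator is recorded days, although the numerator now covers all 84. Two programmers could follow the text and class the same treatment failure in opposite ways, on the first-listed secondary endpoint. The same value enters the primary analysis.

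Three smaller points arise in the same place:

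- A patient with under 10 diary days who is outside the placebo-fill rule is classed only by whether baseline is at least twice the own-arm mean. The recorded days play no part.
- A window with no diary days, or one never opened because its dose was not given (SAP 6.1.3), has no clear rule.
- The planned responder output has no interval, in a trial that stopped at 87 of 172 planned patients.

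**Working it through.** **Inputs from the documents.** N = 84 or 28; formulas A and B; the 10-day threshold; planning difference 2.0 days, SD 4.4 and 10% discontinuation (Protocol 16.1, new wording of Section 9.1). The plan gives no figure for the responder endpoints. Its sample size reproduces: the t-test solution is 76.95, so 77 per group; 77/0.9 = 85.6, so 86 per group and 172 in all. This point does not affect it.

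**Assumed.** Baseline B normal(15, 5) truncated to 8-28; placebo average P from 9 to 11; arm means 9 (active) and 11 (placebo) in step 5; drop-out spread evenly over 84 days; 43 per arm.

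**1. One unchanged patient, 12-week window.** B = 15, X = 28 diary days with 15 headache days, P = 11. The filled total as written is 15 + 56 × 11/84 = 22.33.

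| Reading | Value per 28 days | Change from baseline |
|---|---|---|
| (i) total × 28/84 | 7.44 | 50.4% reduction, responder |
| (ii) formula A: total × 28/28 recorded days | 22.33 | 48.9% increase |
| (iii) daily-rate fill: (15 + 56 × 11/28) × 28/84 | 12.33 | 17.8% reduction |

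At P = 10 the results are a 51.9% reduction, a 44.4% increase and a 22.2% reduction. Reading (ii) can give impossible values: with B = 16, P = 12, X = 14 and 8 headache days, (8 + 70 × 12/84) × 28/14 = 36 days in 28. In a 4-week window N = 28, the fill is already a daily rate, and there is no scale error.

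**2. How often an unchanged discontinuer passes.** For X below 42, reading (i) needs B ≥ (84−X)P / [3(42−X)] and reading (iii) needs B ≥ (84−X)P / (42−X). For larger X neither can be met. Averaged over X = 1 to 83:

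| P | Reading (i) | Reading (iii) |
|---|---|---|
| 9 | 36.6% | 3.1% |
| 10 | 34.5% | 1.4% |
| 11 | 32.4% | 0.5% |

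**3. Effect on the 12-week comparison.** Simulation with 300,000 per arm, mean changes −6 and −4, SD 4.4 and 10% drop-out. With half the drop-out for the three named reasons and half of those patients unchanged, reading (i) gives 37.0% vs 22.3% and reading (iii) 34.9% vs 22.3%. The differences are 14.7 and 12.6, a gap of 2.1 points. With 25-75% of drop-out for those reasons and 0-100% of those unchanged, reading (i) exceeds a full non-responder coding by 0.9 to 3.5 points. That coding differs from reading (iii) by less than 0.5 points, so the divisor accounts for roughly 1 to 4 points.

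**4. Primary endpoint.** The step 1 patient contributes a change of −7.56, +7.33 or −2.67 days. Against reading (iii), one such patient among 43 moves the active mean by (12.33−7.44)/43 = 0.11 days downwards or (22.33−12.33)/43 = 0.23 days upwards. The planning difference is 2.0 days.

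**5. Own-arm mean.** A patient passes if B is at least 18 (active) or 22 (placebo), with probability 29.5% or 8.3%. In Month 1 and in the 12-week window, 10/84 = 11.9% of drop-outs have under 10 days. Active patients under the placebo fill (fraction f of drop-outs) are not affected. The shift in the between-arm difference, against non-responder coding, is 0.10 × 0.119 × [(1−f) × 0.295 − 0.083]. This is 0.16 points at f = 0.25 and −0.01 at f = 0.75. For Months 2 and 3 the ceilings are 0.10 × 38/84 × 0.212 = 0.96 and 0.10 × 66/84 × 0.212 = 1.66 points. They are ceilings because they give the own-arm mean to every active drop-out and count windows whose dose was never given.

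**6. No diary days.** The fill needs X > 0, so an active-arm failure with an empty window could fall to the under-10-days bullet and receive the active mean. The baseline needed is then 18, not the 22 implied by the placebo mean.

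**7. Interval.** For assumed rates of 35% and 25% at 43 per arm, the half-width is 1.96 × √(0.35 × 0.65/43 + 0.25 × 0.75/43) = 0.193, about 19 points.

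**The case against.** Protocol 9.5.5.1 describes the imputed quantity as a proportion of days in the rest of the window. That supports a daily rate, and a careful programmer might choose it. This stands as evidence of intent, but it does not settle the matter: SAP 1.6 speaks of an average number instead, and the SAP introduction says the SAP prevails where the two differ.

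A reader might infer from step 5 that the plan uses a different response criterion in each arm. It does not. The 50% threshold and the under-10-days rule are worded alike for both arms. Only the baseline at which an imputed patient passes differs, and only when the arm means differ. The diary completion rules (Protocol 5.8 and 6.1) should also confine such windows largely to drop-outs. The effect is small and its sign can reverse.

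Recoding every discontinuer for the three reasons as a non-responder gains little once the divisor is right. In the central scenario the difference is 12.7 points, against 12.6 with the daily-rate fill. That objection stands, so full recoding belongs in a sensitivity analysis.

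SAP 6.3.1 does not forbid an interval, and key status is itself inconsistent. SAP 6.3 with 1.2 makes this endpoint key, while Section 7 words the tested endpoint as headache days of any severity. The interval is therefore an omission to repair; the documents do not show that it was withdrawn.

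If the ANCOVA/MMRM lead-in governs instead of the Note, the responder endpoints have no stated missing-data rule, and the SAP still needs correcting.

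**Conclusion.** The 12-week placebo fill is wrong as written and must be corrected for the primary endpoint as well as the responder endpoints. That follows from the SAP's own definitions. The sizes rest on the assumed baselines, placebo means and drop-out pattern: about 32-37% of unchanged active-arm discontinuers pass as 12-week responders under reading (i), against 0.5-3.1% with a daily rate, and the between-arm difference grows by roughly 1 to 4 points at 10% drop-out.

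A reader might infer that the plan favours fremanezumab. The documents do not support that: reading (ii) works against the active arm, and nothing says which reading will be programmed. Nor is the whole primary analysis undermined. Only active-arm patients who stop for the three named reasons are affected, and the sensitivity MMRM uses monthly windows, which are free of the scale error.

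The own-arm mean is secondary: about 0 to 0.2 points in Month 1 and the 12-week window, with ceilings of about 1.0 in Month 2 and 1.7 in Month 3. The empty-window gap and the missing interval are real and easily closed.

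**What to change.** **SAP 6.1.4, for the primary and the responder endpoints.** Fill each missing day at the placebo monthly average divided by 28. Divide the filled 12-week total by 84, then multiply by 28. State what happens when X = 0, and make the lead-in agree with the Note.

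**SAP 6.3.1 and 6.3.2.** Use all FAS patients as the denominator. In either arm, count a patient with under 10 diary days in the window as a non-responder, including one with none or with no window because the dose was not given. Keep the corrected placebo fill for active-arm discontinuers with 10 or more days. Coding all discontinuers for lack of efficacy, adverse event or death as non-responders can be a sensitivity analysis.

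**Reporting.** Add the Mantel-Haenszel risk difference stratified by PTH onset with its 95% confidence interval, and reconcile the key secondary list between SAP 6.3/1.2 and Section 7.

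**Cost.** SAP wording, programming and one added statistic. Responder rates will be slightly lower, and some truly improved patients with sparse diaries will count as failures.
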